8.4 Sample Size

The sample size for the phase 1 part will depend on the observed DLT at each dose levels. The phase 1 expansion cohort will use 9 evaluable patients. The table below provides the probability of observing DLT in $\geq 33\%$ in 9 patients based on the binomial distribution. If the true DLT rate is as low as 5%, such a probability is small, only 0.0084 but if the true DLT is 50%, such a probability is very high at 0.91.

True DLT	probability of observed DLT $\geq 33\%$ in 9 patients
1%	0.000084
5%	0.0084
10%	0.053
20%	0.262
30%	0.537
40%	0.768
50%	0.91

The sample size for the phase 2 portion of the study was determined using the following calculations. A total of 88 (14 are expected to have positive margins after standard breast surgery) simultaneously achieves 84.7% power to detect an expected sensitivity of 0.95 against an unacceptable sensitivity of 0.7 and 100% power to detect an expected specificity 0.95 against an unfavorable specificity of 0.7 using a one-sided binomial test. The target significance level is 0.05. The actual significance level achieved by the test on sensitivity is 0.0475 and achieved by the test on specificity is 0.041. The current recall rate (i.e., margin positivity rate) after the use of cavity shave margin is ~19% ³⁶, which agrees with the best practices in Washington University, ~15.5%. 88 patients allows 92.66% power to test a reduction in positive margin rate from 15.5% to 5% based on a one-sided Binomial exact test at a 5% level.

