5.2.1.4 Dose Escalation Criteria

The molecular probe LS301 is an imaging agent binding to breast cancer cells and other malignant cells and will be visualized through by CVG which is a non-significant risk device. Similar to the FDA-approved agent ICG, we do not expect any serious adverse events caused by the agent.

A rolling six design will be used for the phase 1 portion. In the rolling six design, 2 to 6 patients can be enrolled to a dose each time. The dose de-escalation occurs when two or more DLTs occur at a dose level, while dose escalation occurs with 3/3, 4/4, 5/5, 5/6, or 6/6 patients are evaluated without DLT. (Refer to Section 8.1 for further details.)

5.2.2 Phase 2

After data from the phase 1 portion of the study have been submitted to and reviewed by the FDA, and if analysis of the data from phase 1 confirms the safety of administering LS301 in humans and establishes the optimal imaging dose, 88 patients will be enrolled in the phase 2 portion of the study after any necessary protocol revisions have been made based on phase 1 data and FDA approval.

It is expected that the study procedures for phase 2 will be the same as the procedures in phase 1. The optimal imaging dose of LS301 determined in phase 1 will be administered in phase 2.

The breast tissue and axillary LNs will be imaged non-invasively using the CVG and worn by a non-operating member of the surgical team. After removal of the breast cancer and SLNs using current best practice, a member of the surgical team who is not conducting the surgery will wear the CVG to determine if LS301 fluorescence is present at the margin and in SLNs, using a global threshold of 20% signal above background or a dynamic statistical threshold to indicate a positive margin. The accuracy of determining margin positivity will be established by comparing the CVG assessment to histopathology.

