8.3.2 Margin Positivity and SLN Positivity Prediction Analysis

Margin positivity as determined by LS301 and CVG will be tabulated with the gold standard histopathological examination results as the table shown below.

		Histopathology results		
		Negative	Positive at CVG identified locations	Positive at other unidentified locations
CVG results	Negative	n_{11}	0	n_{13}
	Positive at CVG identified locations	n_{21}	n_{22}	0

Diagnostic test operating characteristics including sensitivity, specificity, overall accuracy, positive and negative predictive value will be calculated. The true positives ($=n_{22}$) are the tumors which show positive margins at any location agreed by both the histopathology examination and by LS301 and CVG. Specificity is defined as the proportion of tumors with histopathologically confirmed negative margins which are called to have negative margins by LS301 and CVG, calculated as $n_{11}/(n_{11}+ n_{21})$. Sensitivity is defined as the proportion of tumors which are predicted to have positive margins by LS301 and CVG among the tumors with histopathologically confirmed positive margins both at CVG identified locations and at other locations unidentified by CVG, calculated as $n_{22}/(n_{13}+n_{22})$. Overall accuracy is defined as the proportion of tumors with margin positivity/negativity correctly predicted by the CVG among all tumors, calculated as $(n_{11}+ n_{22})/(n_{11}+n_{13}+ n_{21}+n_{22})$. Positive predictive value is defined as the proportion of tumors with margins called positive at LS301 and CVG identified locations by the histopathology examination among all those predicted to have positive margins by CVG, calculated as $n_{22}/(n_{21}+n_{22})$. Negative predictive value was defined as the proportion of tumors with truly negative margins among those predicted so by CVG, calculated as $n_{11}/(n_{11}+ n_{13})$. The margin positivity rate based on LS301 and CVG will be estimated as $n_{13}/(n_{11}+n_{13}+ n_{21}+n_{22})$. All the estimates will be accompanied with 95% confidence interval. Margin positivity rate will be compared against the current 15.5% margin positivity rate using the two-sided one-sample binomial exact test. Given enough DCIS and invasive breast cancer (IBC), similar diagnostic characteristics will be calculated separately in the subset tumors of DCIS and IBC.

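### The 84.7% and 92.66% powers in 8.4 assume exactly 14 positive margins and a one-sided test. The design fixes only 88 patients, and 8.3.2 tests two-sided. The corresponding powers are 66.5% to 79.0% and 84.9%.

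*Combined protocol and SAP*

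**What the plan says.** Section 8.4 (Sample Size) justifies the phase 2 size in two ways.

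- **Sensitivity and specificity.** A total of "88 (14 are expected to have positive margins after standard breast surgery) simultaneously achieves 84.7% power" for sensitivity 0.95 against 0.70, and 100% power for specificity 0.95 against 0.70. The tests are one-sided binomial with target level 0.05 and attained levels 0.0475 and 0.041.
- **Margin positivity rate.** The 88 patients give "92.66% power to test a reduction in positive margin rate from 15.5% to 5% based on a one-sided Binomial exact test" at a 5% level.

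For the current positive-margin rate, 8.4 offers two figures: "The current recall rate (i.e., margin positivity rate) after the use of cavity shave margin is ~19"%, and about 15.5% as best practice at Washington University.

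Section 5.2.2 (Phase 2) sets enrolment by patients: "88 patients will be enrolled in the phase 2 portion of the study after any necessary protocol revisions have been made". No rule secures a given number of positive margins.

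Section 8.3.2 defines sensitivity as n22/(n13+n22), so its denominator is the observed number of histology-positive tumours. It compares the margin rate, n13 over all tumours, with 15.5% "using the two-sided one-sample binomial exact test" and states no alpha. For the other measures it says only this: "All the estimates will be accompanied with 95% confidence interval". It gives no interval method, no test against 0.70 and no success rule.

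**The concern.** Sensitivity for positive margins is the quantity that limits N, because only about one patient in six contributes to it. A reader of 8.4 will take the chance of showing sensitivity above 0.70, when it is truly 0.95, to be about 85%. That figure treats 14 positives as given, but the design leaves their number to chance, and the exact test is very uneven in that number.

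The margin-rate test is described in two incompatible ways. An observed 7/88 would be significant under 8.4 but not under 8.3.2 at two-sided 0.05.

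The tests that justify N = 88 are also missing from the analysis section. If the confidence interval were used in their place, the conclusion at 13/14 could turn on an interval method chosen after the data are seen.

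**Working it through.** **Inputs.** From 8.4: N = 88; 14 expected positives (74 negatives); sensitivity and specificity 0.95 against 0.70; one-sided 0.05; prevalence of positive margins 15.5% or 19%; margin rate 15.5% reduced to 5%. From 8.3.2: two-sided exact test for the margin rate. Assumed: two-sided alpha 0.05, since 8.3.2 gives none.

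**1. The plan's figures reproduce.**

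- Sensitivity, n = 14, reject at 13 or more. Alpha = 14(0.7^13)(0.3) + 0.7^14 = 0.0407 + 0.0068 = 0.0475. Power = 14(0.95^13)(0.05) + 0.95^14 = 0.3593 + 0.4877 = 0.8470.
- Specificity, n = 74, reject at 59 or more: alpha 0.0410, power above 0.9999.
- Margin rate, N = 88, reject at 7 or fewer: P(X ≤ 7 | 0.155) = 0.0280, power P(X ≤ 7 | 0.05) = 0.9266.

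**2. Sensitivity power when the number of positives M is random.** M follows Binomial(88, prevalence), with mean 88 × 0.155 = 13.64 or 88 × 0.19 = 16.72. For each M, take the smallest critical value with exact one-sided alpha at most 0.05:

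| M | Reject at | Power at 0.95 | P(M) at 15.5% | P(M) at 19% |
|---|---|---|---|---|
| ≤ 8 | never (0.7^8 = 0.058) | 0 | 0.058 | 0.009 |
| 12 | 12 | 0.540 | 0.109 | 0.050 |
| 13 | 13 | 0.513 | 0.117 | 0.069 |
| 14 | 13 | 0.847 | 0.115 | 0.087 |
| 15 | 14 | 0.829 | 0.104 | 0.101 |
| 18 | 17 | 0.774 | 0.049 | 0.099 |
| 19 | 17 | 0.934 | 0.033 | 0.085 |

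Averaged power = Σ P(M = m) × power(m):

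- 15.5%: **0.665**
- 14/88 = 15.9%: 0.683
- 19%: **0.790**
- 20%: 0.816

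Fewer than 14 positives occur with probability 0.497 at 15.5% and 0.193 at 19%. The realised M gives power of at least 84.7% with probability 0.195 and 0.394. Specificity power, averaged in the same way, stays above 0.9999.

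**3. Margin-rate test, two-sided.** At 7/88 the exact p-value is 0.056 (doubled tail) or 0.054 (minimum likelihood). At 6/88 it is 0.024 or 0.026. The cutoff at 0.05 is therefore 6, and power P(X ≤ 6 | 0.05) = **0.849** under either definition.

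**4. What the 5% alternative means.** The endpoint is n13/N, so a 5% rate at 15.5% prevalence corresponds to sensitivity 1 − 0.05/0.155 = 0.677. At sensitivity 0.95 the rate is 0.155 × 0.05 = 0.8%, and power exceeds 0.9999 with either sidedness.

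**5. Intervals at 13/14.** This is the smallest result at M = 14 that the power calculation counts as success. The lower two-sided 95% limit is 0.661 (Clopper-Pearson), 0.685 (Wilson), 0.712 (Jeffreys) or 0.794 (Wald). The one-sided 95% Clopper-Pearson limit is 0.703, which agrees with the test in 8.4.

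**The case against.** Section 8.4 discloses the expected 14 in the same sentence as the power, and powering sensitivity at the expected number of positives is common practice. Many other counts also do well: power is 77% to 85% for 14 to 18 positives and 89% or more for 19 to 24. This stands, and 8.4 contains no arithmetic error. It does not make 84.7% the power of a design that fixes 88 patients.

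Much of the drop comes from the discreteness of the exact test. Averaged attained alpha at 15.5% is only about 0.025, and a mid-p test would average 0.794 at 15.5% and 0.875 at 19%. This also stands, but the attained 0.0475 in 8.4 shows that the plan uses the ordinary exact test.

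Section 1.11 puts current margin positivity above 20%, and averaged power is 0.816 at 20% and 0.850 at 21.5%. In addition, 15.5% is a Washington University figure, while phase 2 runs at UT Southwestern. The true rate at the phase 2 site is therefore uncertain. Even so, 15.5% is the rate that fits 14 expected positives and is the null value for the margin test.

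On the margin rate, 84.9% depends on the assumed alpha. At two-sided 0.10 the cutoff would stay at 7/88 and 92.66% would be unchanged. The 95% intervals in 8.3.2 make 0.05 the more natural reading. Power is ample if sensitivity is 0.95, so the loss in power matters less here than the conflict over the decision rule.

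Finally, 8.4 does name the one-sided test and its null values, and under that test 13/14 rejects. The interval ambiguity arises only if the interval replaces the test, and 8.3.2 leaves that open.

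**Conclusion.** The concern holds. Both stated powers are correct under their own conditions, but those conditions are not the ones the plan sets elsewhere.

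- **Sensitivity.** With 88 patients fixed, averaged power is 66.5% at 15.5% prevalence and 79.0% at 19%, against 84.7% stated. This assumes a binomial number of positives, all 88 tumours evaluable, and the one-sided 5% exact test applied to the observed count. This is the most consequential part.
- **Margin rate.** Sections 8.3.2 and 8.4 contradict each other on sidedness, and so on whether 7/88 is a significant result. With the two-sided test at an assumed 0.05, power at the 5% alternative is 84.9%, against 92.66% stated.
- **Analysis section.** The sensitivity and specificity tests that justify N = 88 are not carried into 8.3.2.

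The specificity power is unaffected. This should be fixed before phase 2 opens.

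**What to change.** 1. In 8.4, label 84.7% as conditional on exactly 14 positive margins. Add the averaged power, about 67% at 15.5% and 79% at 19%, and state whether it is accepted.
2. In 8.3.2, add the one-sided 5% exact tests of sensitivity and specificity against 0.70, applied to the observed numbers of positives and negatives. Report matching one-sided 95% exact limits, and name the method for any other interval.
3. Give the margin-rate test the same sidedness and a stated alpha in 8.3.2 and 8.4. If it stays two-sided at 0.05, restate its power as 84.9% at the 5% alternative.

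The cost is a few sentences and a less favourable stated power. No extra patients are required. Raising N is a separate choice for the sponsor: averaged power of 80% needs about 111 evaluable tumours at 15.5% or 90 at 19%, before any allowance for patients outside the efficacy set in 8.6. Section 5.2.2 already provides a revision point before phase 2 at which all of this can be settled.

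### Section 8.3.2 omits the sensitivity and specificity tests that size phase 2, and its only formal efficacy test can be passed by a device of no diagnostic value

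*Combined protocol and SAP*

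**What the plan says.** Section 8.4 (Sample Size) bases phase 2 on 88 patients, 14 of them expected to have positive margins. It says this number "simultaneously achieves 84.7% power to detect an expected sensitivity of 0.95 against an unacceptable sensitivity of 0.7", and gives "100% power to detect an expected specificity 0.95 against an unfavorable specificity of 0.7", both "using a one-sided binomial test. The target significance level is 0.05". It adds: "The actual significance level achieved by the test on sensitivity is 0.0475 and achieved by the test on specificity is 0.041". A further sentence concerns the margin rate: "88 patients allows 92.66% power to test a reduction in positive margin rate from 15.5% to 5% based on a one-sided Binomial exact test", at the 5% level.

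Section 8.3.2 sets out the analysis. Sensitivity, specificity, accuracy and the predictive values are computed from a table of CVG result against histopathology. Then: "All the estimates will be accompanied with 95% confidence interval". The section contains no null value of 0.70, no test of sensitivity or specificity, and no rule for a positive conclusion. The only hypothesis test it names compares the margin positivity rate with 15.5%, using an exact binomial test that is two-sided.

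Sections 8.2.2 and 8.3.2 define that rate as n13/N: tumors with a histologically positive margin that the CVG missed, divided by all tumors. Section 8.1 allows no intervention on the basis of CVG findings.

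**The concern.** The tests that justify 88 patients are missing from the section that says how the data will be analysed, and the one test found there answers a different question. The CVG cannot change the operation, so n13/N does not measure an improvement in surgical margins. Specificity does not enter it, so it does not measure diagnostic value either. An analyst who follows 8.3.2 as written could report a significant result for a device whose sensitivity is the value that 8.4 treats as unacceptable, or whose specificity is zero. The two sections also disagree on whether this test has one side or two, which changes its rejection limit and its power.

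**Working it through.** **Inputs.** From 8.4: N = 88, 14 positives expected (88 × 0.155 = 13.6), hence 74 negatives; null 0.70 and alternative 0.95 for both measures; one-sided target level 0.05; margin rate 15.5% against 5%. From 8.3.2: the definition of n13/N and the two-sided test. Assumed: a true histologic positivity of 15.5%, and calls made per patient.

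**1. The plan's own figures reproduce.**
- Sensitivity, success if at least 13 of 14: P(X ≥ 13 | 14, 0.70) = 14 × 0.7¹³ × 0.3 + 0.7¹⁴ = 0.0407 + 0.0068 = 0.0475. Power at 0.95 = 0.847.
- Specificity, success if at least 59 of 74: level 0.0410, power above 0.9999.
- Margin rate, one-sided, at most 7 missed of 88: P(X ≤ 7 | 88, 0.155) = 0.0280; power at 5% = 0.9266. At most 8 would have level 0.058.

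**2. What n13/N measures.** Its expected value is prevalence × (1 − sensitivity) = 0.155 × (1 − s). Setting this equal to the 5% target gives s = 1 − 0.05/0.155 = 0.677. The target is therefore met in expectation by a sensitivity below 0.70.

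**3. Sidedness.** Seven missed of 88 gives a two-sided exact p of 0.054 (doubling the one-sided value gives 2 × 0.0280 = 0.056). Six missed gives 0.026. The two-sided limit is therefore at most 6, and power at 5% is P(X ≤ 6 | 88, 0.05) = 0.849, against the stated 0.9266.

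**4. Chance of passing the margin-rate test,** P(X ≤ c | 88, 0.155 × (1 − s)):

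| CVG | Expected n13/N | Two-sided, c = 6 | One-sided, c = 7 |
|---|---|---|---|
| Calls every specimen positive (s = 1, specificity 0) | 0 | 1.00 | 1.00 |
| Coin flip (s = 0.5) | 7.75% | 0.47 | 0.63 |
| s = 0.70 | 4.65% | 0.88 | 0.95 |

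For the all-positive CVG the observed result is always 0/88, with one-sided p = 0.845⁸⁸ = 3.7 × 10⁻⁷.

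**5. Intervals at the success boundary.** At 13/14 the exact 95% interval is 66.1% to 99.8%. The exact 90% interval starts at 70.3% and so agrees with the one-sided 5% test. If an exact 95% interval decided the matter with 14 positives, 14/14 would be needed: level 0.7¹⁴ = 0.0068, power 0.95¹⁴ = 0.488.

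**6. Dependence on the number of positives.** The power of the one-sided 5% sensitivity test is 0.513 with 13 positives, 0.847 with 14 and 0.829 with 15. Averaged over a binomial(88, 0.155) count it is 0.665, about 67%.

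**The case against.** Section 8.4 does name the test, both null values and the level. Sections 8.3 and 8.4 belong to one statistical chapter, so a fair reader can infer that the tests are intended. That stands: the tests are not absent from the protocol. But a sample-size paragraph is not an analysis rule, and 8.3.2 names a different test and no success criterion.

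A CVG that marks everything positive would also be exposed, because specificity is reported from the same table. Section 8.2.2 puts both measures under the primary objective, and section 1.10 calls phase 2 a preliminary evaluation. This also stands. A reader might infer that the sponsor means to claim success on the margin rate alone; nothing in the documents says so. What remains is that no rule prevents it, and that the one p-value planned for efficacy carries little information on diagnostic performance. The case of s = 0.70 is not a degenerate one.

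It is also tempting to read the 95% intervals as cutting power from 84.7% to 48.8%. The documents do not support that. The intervals accompany estimates and are not described as a decision rule. Their method is unstated: at 13/14 the Wilson lower limit (68.5%) falls below 70%, but the Jeffreys limit (71.2%) does not. The exact 5% and 2.5% rules coincide at 11, 12, 13, 17 and 18 positives and differ at 14, 15 and 16. For specificity, power stays above 99.9% under either rule.

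**Conclusion.** The point holds as a mismatch between 8.3.2 and 8.4; the stated powers are correct for the tests that 8.4 describes. As written, the only formal efficacy test ignores specificity and gives a significant result with probability 0.88 for a CVG at the sensitivity the plan calls unacceptable, and 0.47 for a coin flip. These probabilities rest on 15.5% histologic positivity, per-patient calls and the two-sided limit. The conflict over sidedness needs no assumption about a decision rule: the margin-rate power is 92.66% one-sided and 84.9% two-sided. Two secondary qualifications apply. The 48.8% arises only if an exact 95% interval is the decision rule with exactly 14 positives. The 84.7% likewise belongs to exactly 14 positives.

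**What to change.** In 8.3.2:
- State the exact one-sided 5% binomial tests of sensitivity > 0.70 and specificity > 0.70.
- Require both for a positive conclusion on margins. No alpha split is needed because both must pass. With 14 positives and 74 negatives the joint power is 0.847 × more than 0.9999, still about 0.847.
- Report exact 90% intervals, whose lower limits are the matching one-sided 95% bounds, beside the 95% intervals.
- State that n13/N cannot by itself support a conclusion of diagnostic value.

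Make the margin-rate test the same in both sections, or restate its power in 8.4 as 84.9% if it stays two-sided. Add to 8.4 that the 84.7% is conditional on 14 positives and is about 67% when averaged over the count.

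The cost is a few sentences, with no change to sample size or procedures. Section 5.2.2 already foresees protocol revisions before phase 2 opens. Only if the sponsor wants a one-sided 2.5% criterion for sensitivity would the size change: at least 84.7% power then needs 22 positives, or 22/0.155 = about 142 patients.

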1.0 BACKGROUND AND RATIONALE

1.1 Surgical Resection of Breast Cancer and Sentinel Lymph Node Biopsy

Surgical resection is the standard of care for many solid tumors such as breast cancer, and sentinel lymph node (SLN) biopsy is used for cancer staging¹. Before breast surgery, standard imaging methods including mammography and ultrasound are used to identify tumor location. However, these preoperative imaging methods are not able to provide real-time image guidance in the operating room to ensure complete removal of tumors or assess surgical margins. Unfortunately, incomplete tumor removal increases the chances of cancer recurrence by two-fold² and necessitates repeat surgery, whereas inaccurate SLN identification may misdiagnose the cancer stage. Despite recent advances in pre-operative imaging methods, surgeons rely on visual inspection, palpation, and tactile evaluation to distinguish cancer from uninvolved tissue intraoperatively, leading to subjective decision-making and variable outcomes. For example, up to 70%³⁻⁵ of patients undergoing breast-conserving reconstructive surgery (BCS) have positive margins, depending on where the surgery was performed, experience of the surgeon, and the tumor characteristics⁶⁻⁸. For these reasons, we seek to develop an image-guided method for differentiating tumors from surrounding tissues and offer real-time surgical navigation^{10,11}.

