4.0 REGISTRATION PROCEDURES

Patients must not start any protocol intervention prior to registration through the Siteman Cancer Center for phase 1A and UT Southwestern Medical Center Velos database for phase 1B and phase 2.

The following steps must be taken before registering patients to this study:

1. Confirmation of patient eligibility
2. Registration of patient in the Siteman Cancer Center OnCore database for phase 1A and UT Southwestern Medical Center Velos database for phase 1B and phase 2.
3. Assignment of unique patient number (UPN)

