8.0 STATISTICAL CONSIDERATIONS

8.1 Study Design

A rolling six design which is intended for relatively safe trials and shortening the study duration is proposed for the phase 1 portion ⁷⁴. In the rolling six design, three to six patients can be enrolled to a dose each time. The dose de-escalation occurs when two or more DLT occur at a dose level while dose escalation occurs when 3/3, 4/4, 5/5, 5/6 or 6/6 patients are evaluated without DLT ⁷⁵. Three dose levels will be tested in the phase 1 study, 0.05, 0.075 and 0.10 mg/kg. LS301 will be administered intravenously at a starting dose of 0.05 mg/kg to a cohort of six patients and escalate/de-escalate following the decision rule of the rolling six design. Once six patients have been included at the current dose level, inclusions are suspended until at least five of the six patients have completed the procedure without DLT observed in the evaluation period. MTD is hit where two or more patients out of six at a dose level experience DLT. We do not expect any serious adverse events related to LS301 at the initial Dose Level 1. Once the MTD is determined, an expansion cohort with 9 patients will be tested at the MTD and an optimal imaging dose will be recommended for the subsequent phase 2 trial.

At the completion of the expansion cohort, a single arm phase 2 trial will be performed at the optimal imaging dose. A breast surgeon will perform breast conserving surgery per standard of care. At the completion of the surgery, a second investigator (to reduce bias in data collection) will wear the cancer vision goggle (CVG) to visualize the excised tissue to determine if there are any positive margins based on the presence of LS301 fluorescence. If any positive margins are observed, the subject will be considered to have a positive margin; otherwise, the margin is considered negative. The excised tissue will later be examined by a breast cancer pathologist. Standard pathologic techniques will be used to determine if there are positive margins. Particular attention will be paid to the sites marked following CVG assessment to confirm whether the margin is positive or negative at any of these sites, or positive at other locations not identified by CVG. No interventions will be allowed based on the CVG results.

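### The margin-rate test in phase 2 uses a fixed 15.5% taken from Washington University, while phase 2 is assigned to UT Southwestern, so the test mixes the site's own rate with the device effect

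*Combined protocol and SAP*

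**What the plan says.** Section 8.4 sets phase 2 at 88 patients: "A total of 88 (14 are expected to have positive margins after standard breast surgery"). On that count it claims "84.7% power to detect an expected sensitivity of 0.95 against an unacceptable sensitivity of 0.7", near-certain power for specificity, and 92.66% power to show a fall in the margin rate from 15.5% to 5%. It cites about 19% from a published source and then adopts the lower figure: "which agrees with the best practices in Washington University, ~15.5" percent.

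Section 8.3.2 carries the figure into the analysis: "Margin positivity rate will be compared against the current 15.5% margin positivity rate using the two-sided one-sample binomial exact test". The quantity tested is n13/N, the share of all tumours whose margin is positive on histology but was not flagged by the CVG.

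Section 4.0 registers patients through Washington University for phase 1A and the "UT Southwestern Medical Center Velos database for phase 1B and phase 2". Sections 6.2, 7.2 and 5.9 place phase 2 reporting, monitoring and closure at UT Southwestern as well. Section 1.1 says positive margins vary "depending on where the surgery was performed, experience of the surgeon, and the tumor characteristics". Section 8.1 adds: "No interventions will be allowed based on the CVG results".

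**The concern.** A one-sample test treats its null value as the known rate that would apply without the device. Here that value comes from one hospital and the patients come from another. The documents give no UT Southwestern rate and no argument for carrying 15.5% over, and their own background section names place of surgery as a source of variation.

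If the UT Southwestern surgeons leave fewer positive margins than 15.5%, the missed rate can fall below the benchmark with little help from the device. If they leave more, a useful device can fail to beat it. In both cases a difference between hospitals is read as a property of LS301 and the CVG.

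The same rate appears to set the number of histologically positive cases, which drives the sensitivity power.

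**Working it through.** **Inputs.** N = 88; null rate 15.5%; sensitivity 0.95 against 0.70; one-sided 5% for power (Section 8.4). Two-sided exact test and cell definitions from Section 8.3.2. The documents give no UT Southwestern rate, so every site rate other than 15.5% below is an assumption.

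**1. The plan's figures reproduce.**
- Expected positives: 88 × 0.155 = 13.64, rounded to 14. The cited 19% would give 88 × 0.19 = 16.7. That the 14 rests on 15.5% is thus an inference from arithmetic.
- Sensitivity, n = 14, reject at 13 or more: P(X ≥ 13 | 14, 0.70) = 0.0475; P(X ≥ 13 | 14, 0.95) = 0.847.
- Specificity, n = 74, reject at 59 or more: size 0.041, power above 0.9999.
- Margin rate, n = 88, reject at 7 or fewer, one-sided: size 0.028; P(X ≤ 7 | 88, 0.05) = 0.9266.

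The arithmetic is sound. The question is whether the input applies to the enrolling site.

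**2. The margin-rate test as a function of the site's rate.** With site rate p and sensitivity s, the expected missed rate n13/N is p(1 − s). The planned two-sided exact test rejects on the low side at 6 or fewer of 88 (p-value 0.026 at 6, 0.054 at 7).

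For a CVG that detects nothing, s = 0 and the missed rate is p itself:

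| Site rate p | P(X ≤ 6 of 88) |
|---|---|
| 10% (assumed) | 21% |
| 15.5% | 1.2% |
| 19% (assumed for this site) | 0.1% |

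For a CVG with s = 0.70:

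| Site rate p | Missed rate p × 0.30 | P(X ≤ 6 of 88) |
|---|---|---|
| 15.5% | 4.65% | 88% |
| 25% (assumed) | 7.5% | 51% |

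The same device gives different answers according to the hospital's own rate.

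**3. Sensitivity power as a function of the site's rate.** The number of positives n is random, Binomial(88, p). Averaged power is the sum over n of P(n) × P(X ≥ c(n) | n, 0.95), where c(n) is the exact one-sided 5% critical value against 0.70.

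| Site rate p | Expected positives | Averaged power |
|---|---|---|
| 10% (assumed) | 8.8 | 32% |
| 12% (assumed) | 10.6 | 47% |
| 15.5% | 13.6 | 66.5% |
| 19% (assumed for this site) | 16.7 | 79% |
| 25% (assumed) | 22.0 | 91% |

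The 84.7% is the power with exactly 14 positives. With 13, all 13 must be detected and power is 0.95^13 = 51.3%. The fall from 84.7% to 66.5% therefore occurs at 15.5% itself and comes from the random count. The site effect is the spread around 66.5%. Specificity power stays near 100% for 62 to 79 negatives.

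**4. The comparator is already in the trial.** CVG findings may not alter surgery (Sections 1.10, 5.2.4 and 8.1). In the Section 8.3.2 table, (n13 + n22)/N is therefore the standard-of-care positive-margin rate in the same patients, operated on by the same surgeons.

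**The case against.** The strongest reply is that 15.5% is the lowest current-practice rate in the documents, beside about 19% (Section 8.4), above 20% (Section 1.11) and up to 70% (Section 1.1). On those figures it is a cautious null: at 19% or 20%, averaged sensitivity power rises to 79% or 82%, and a useless CVG is almost never declared a reduction. The unfavourable figures need a site rate of about 10% to 12%, for which the documents give no support. This stands, and it is why the direction of error must be left open. It does not rescue the test, because a higher site rate brings the opposite error, 51% instead of 88% for the same device.

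The plan would also not be misled by a useless device on this test alone. Sensitivity is tabulated alongside and would be zero, and no section makes the margin-rate test a stand-alone success rule. This stands too. It limits the harm to what the margin-rate comparison can be said to show.

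Replacing the benchmark by a paired test would not help. The difference between (n13 + n22)/N and n13/N is n22/N, which cannot be negative. At a 15.5% rate, a CVG with only 10% sensitivity gives n22 of at least 1 in 1 − (1 − 0.0155)^88 = 75% of trials. This stands and shapes the fix.

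On the facts, only phase 1B is expressly said to be conducted at UT Southwestern (Section 5.2.1). For phase 2 the site follows from registration, reporting, monitoring and closure. These agree with one another, and Washington University is assigned phase 1A only.

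**Conclusion.** The concern holds as a mismatch between the source of the benchmark and the site that supplies the patients. The 15.5% comparison cannot be read as a device effect, and the 84.7% sensitivity power is not supported for the enrolling site. The sizes are those tabulated above. They rest on assumed site rates and on the inference that the 14 comes from 15.5%.

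A reader might go further in three ways that the documents do not support:
- That 15.5% is too high for UT Southwestern, so that the trial is underpowered or biased towards success. No rate is given for that site, and the error could run either way.
- That the whole gap between 84.7% and 32% at a 10% rate is due to the hospital. The part down to 66.5% is present at 15.5%.
- That all the stated power fails. Specificity power is unaffected.

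**What to change.** 1. In Section 8.3.2, report the concurrent standard-of-care rate (n13 + n22)/N beside the missed rate n13/N, each with an exact 95% confidence interval. Base the device conclusion on sensitivity, n22/(n13 + n22). Keep 15.5% only as a descriptive external benchmark. Do not test the difference between the two rates against zero.
2. In Section 8.4, before phase 2 opens, justify 15.5% for UT Southwestern or replace it with that site's histological positive-margin rate. Restate expected positives, sensitivity power (averaged over the random number of positives) and, while it is still quoted, margin-rate power over a range on both sides of 15.5%. Section 5.2.2 already foresees protocol revision before phase 2, so there is a natural point for this.

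The cost is a small look-up of site data and some rewording. The stated power will probably look less favourable, and the margin-rate comparison is lost as a formal hypothesis.
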